6.5 Concomitant Medications/Treatments

All medications taken by a subject for the 30 days prior to enrollment will be documented in the study record. All concomitant medications that are administered during the study must be used for the treatment of an AE (other than oral contraceptives) and must be recorded in the eCRF for each subject and in the subject's source documents. All medications (other than acetaminophen) must be authorized by the clinic PI (or designee).

7 STUDY SCHEDULE

7.1 Day -21 to Day -2 (Screening)

After providing written informed consent, each subject will be assigned a screening number and undergo an eligibility screening. The following will be obtained during the screening period (within 21 days prior to administration of the study product):

- Review inclusion and exclusion criteria;
- Obtain medical history including current medical diagnoses, major surgical procedures, and medication history including prescription and nonprescription medication (i.e. dietary supplements or herbal medications taken within 30 days prior to Day 1);
- Obtain history of alcohol use, abuse, or dependence;
- Record demographics including date of birth, gender, ethnicity and race;
- Complete a physical examination including vital signs (SBP and DBP, pulse rate, respiration rate, and oral temperature after being supine for 10 minutes), orthostatic blood pressure and pulse rate (taken after 2 minutes in standing position), height, weight, and calculation of BMI. If abnormal, these measurements may be repeated once;
- Obtain blood samples for clinical chemistry, hematology, coagulation tests, urinalysis, serum and urine pregnancy tests (if female), FSH (if post-menopausal), HIV, hepatitis B surface antigen, and hepatitis C antibody;
- Obtain urine sample for drugs of abuse and cotinine; (see [Section 8.2.1](#));
- Obtain urine test for alcohol;
- Obtain 12-lead ECG;
- Distribute a fecal occult blood card with instructions for use and return of card to the clinic on or before Day - 1;
- Review concomitant medication usage.

7.2 Enrollment/Baseline

7.2.1 Day -1 (Admission to Clinic; approximately 24 hours prior to dosing)

Eligible subjects will return to the clinic on Day -1 for the procedures listed below.

- Review inclusion/exclusion criteria. If screening criteria are satisfied, the subject may be admitted to the clinic.
- Confirm that subject adhered to dietary restrictions for previous 72 hours;
- Complete an abbreviated physical examination (general appearance, heart, lungs, skin, and abdomen), skin and oropharyngeal mucosa for evidence of bleeding and/or bruising (oral [gums] and evidence of hematoma, ecchymosis or petechia) and brief neurological examination (mental status, motor system, and sensory system);
- Obtain vital signs (blood pressure, pulse rate, after being supine for 10 minutes, and orthostatic blood pressure and pulse rate (taken after 2 minutes in the standing position), respiratory rate and oral temperature;
- Obtain weight;
- Obtain urine sample for drugs of abuse and cotinine;
- Obtain urine test for alcohol;
- Obtain serum and urine pregnancy tests (if female);
- Obtain baseline clinical chemistry, hematology, coagulation, and urinalysis. Must have no values that are Grade 2 or higher based on the toxicity grading scale in Appendix II;
- Obtain fecal occult blood assessment from kits sent home at screening (if not already assessed). Must have at least 1 negative and no positive values;
- Obtain 2nd 12-lead ECG (Day -1) on the morning of admission. All remaining in-clinic ECGs are obtained at the same time each day during treatment period (within a 2 hour window of the previous ECG);
- Telemetry for at least 4 hours while awake;
- Sham dose consisting of masking solution, 240 mL (total volume) of diluent will be administered on Day -1; subjects must be able to comply with dose solution (30 mL), the 50 mL rinse of dosing container with tap water immediately after dose and the 160 mL of tap water for enrollment into the study;
- Review concomitant medication usage;

7.3 Treatment Period

The specific order of evaluations conducted during the treatment period will be defined by the [REDACTED] Biometrics system.

7.3.1 Day 1

Prior to the administration of the first dose of study product, the following procedures will be performed:

- Brief physical examination focused on the examination of skin and oropharyngeal mucosa for evidence of bleeding and/or bruising (oral [gums] and evidence of hematoma, ecchymosis or petechia), brief neurological examination (mental status, motor system, and sensory system);
- Confirm that subject adhered to fasting requirements of at least 3 hours before the first dosing;
- Obtain vital signs (blood pressure, pulse rate, after being supine for 10 minutes, and orthostatic blood pressure and pulse rate (taken after 2 minutes in the standing position), respiratory rate and oral temperature;
- Obtain a triplicate 12-lead ECG;
- Obtain baseline blood sample for PK analysis ($t=0$), to be taken within 1 hour prior to first dose;
- Telemetry starting at -0.5 hours on Day 1 through at least 4 hours post the first dose;
- Randomization

All subjects will be administered the assigned study product or placebo. The total volume of each dose of the study product solution plus the rinse(s) and water will be 240 mL.

- The following procedures will be instituted to reduce incomplete or interrupted dosing of subjects:
In the event of partial dosing, either due to dosing error, or the subject coughing, gagging or spilling solution, the subject will only be followed for safety measurements as defined in [Section 5.3.3](#).

Following the administration of study product, the following procedures will be performed:

All physical exams, blood tests and ECGs after subjects have been dosed are obtained at approximately the same time each morning (within 2 hours).

- Obtain clinical chemistry, hematology, and coagulation;
- Obtain blood samples for PK analysis at 0.25 (± 5 min), 0.5 (± 5 min), 1 (± 10 min), 1.5 (± 10 min), 2 (± 10 min), 2.5 (± 15 min), 3 (± 15 min), 5 (± 30 min), 6 (± 30 min), 8 (± 30 min) hours (8 hour sample to be collected immediately before the second dose).
- Obtain vital signs (blood pressure and pulse rate including oral temperature and respiratory rate) at 1, 2, 3, 4, 5, 6 and 7 hours (± 15 minutes), after each administration of the study product. Vital signs should be taken after being supine for 10 minutes,

and orthostatic blood pressure and pulse rate (taken after 2 minutes in the standing position);

- Telemetry through at least 4 hours post first dose;
- Obtain fecal occult blood assessment starting approximately 6 hours post first dose on every stool sample. Stool volume and frequency will be recorded;
- Obtain occult blood on all vomitus;
- Perform brief physical examination focused on the examination of skin and oropharyngeal mucosa for evidence of bleeding and/or bruising (oral [gums] and cutaneous) 30 (+ 15) minutes after the first dose;
- Review concomitant medication usage once daily;
- Completed AE assessment (including SAEs) will be recorded on AE source forms throughout the study and placed in the subject's clinic records.

Subjects will receive standardized meals as follows on Day 1: lunch 4 hours post first dose and dinner after completion of procedures scheduled at those times; subjects will also receive a light evening snack. A drink will also be provided with each of the meals. No breakfast will be served on Day 1. Dosing will occur TID every 8 hours \pm 0.5hour.

7.3.2 Day 2 through Day 7 (In-Clinic)

All subjects will be administered the assigned study product or placebo according to the dosing schedule. If a subject has a missed or incomplete dose as described above ([Section 7.3.1](#)) the subject will continue to the next dose as planned. Subjects will not be allowed to miss more than four (4) doses after achieving predicted steady state (i.e. after the third dose on day 1) while participating in the study. If a subject misses four (4) or less doses their continued participation in the study will be determined by the PI and the Emergent and NIAID medical monitors on a case by case basis.

As per Section 7.3.1, all physical exams, blood tests and ECGs after subjects have been dosed are obtained at approximately the same time each morning after dosing (within 2 hours).

- Brief physical examination focused on the examination of skin and oropharyngeal mucosa for evidence of bleeding and/or bruising (oral [gums] and cutaneous); symptom directed/targeted examination based on subject symptoms and brief neurological examination (mental status, motor system, and sensory system);
- Obtain vital signs (blood pressure, pulse rate), after being supine for 10 minutes, and orthostatic blood pressure and pulse rate (taken after 2 minutes in the standing position), respiratory rate and oral temperature;
- Obtain clinical chemistry, hematology, coagulation, and urinalysis;

- Obtain fecal occult blood assessment on every stool sample or less frequent as per discretion of the PI. Stool volume and frequency will be recorded;
- Obtain occult blood on all vomitus
- Obtain 12-lead ECG at same time each day (within 2 hours); telemetry starting 0.5 hours prior to the third (3rd) dose on Day 7 continuously through 4 hours post dose;
- Obtain blood samples for PK analysis Days 2-6: one trough sample daily within fifteen (15) minutes before the first dose approximately the same time each day (± 10 min);
- Obtain blood samples on Day 7: immediately (within fifteen minutes) before the final dose, and at 0.25 (± 5 min), 0.5 (± 5 min), 1 (± 10 min), 1.5 (± 10 min), 2 (± 10 min), 2.5 (± 15 min), 3 (± 15 min), 5 (± 30 min), 6 (± 30 min), 8 (± 30 min), 10 (± 30 min), 12 (± 30 min), and 14 (± 30 min) hours after the final dose;
- Review concomitant medication usage;
- Complete AE assessment (including SAEs) which will be recorded on AE source forms throughout the study and placed in the subject's clinic records. Data from the AE source form will be entered in the Electronic data capture (EDC) system. All AEs will be monitored until they are resolved or determined by the site PI to be medically stable.

7.3.3 Day 8 (Discharge from Clinic)

The following procedures will be performed:

- Abbreviated physical examination (general appearance, heart, lungs, skin, and abdomen), and brief neurological examination (mental status, motor system, and sensory system). Also perform brief physical examination focused on the examination of skin and oropharyngeal mucosa for evidence of for bleeding and/or bruising (oral [gums] and cutaneous);
- Obtain vital signs (blood pressure, pulse rate), after being supine for 10 minutes, and orthostatic blood pressure and pulse rate (taken after 2 minutes in the standing position), respiratory rate and oral temperature; and weight;
- Obtain clinical chemistry, hematology, coagulation, and urinalysis;
- Obtain fecal occult blood assessment prior to discharge if stool available prior to discharge. Subjects may receive a fecal occult blood card per discretion of the PI with instructions for use and return of card to the clinic at a subsequent visit. Stool volume and frequency will be recorded;
- Obtain occult blood on all vomitus

- Obtain 12-lead ECG;
- Obtain blood sample for PK analysis as described in the schedule of events table ([Appendix IV](#));
- Review concomitant medication usage;
- Complete AE assessment (including SAEs) which will be recorded on AE source forms throughout the study and placed in the subjects' clinic records. Data from the AE source form will be entered in the EDC system. All AEs will be monitored until they are resolved or determined by the site PI to be medically stable;
- Discharge from the clinic, with instructions to return on Day 10 ± 1.

7.3.4 Day 10 ± 1 (Outpatient Visit)

The following procedures will be performed:

- Abbreviated physical examination (general appearance, heart, lungs, skin, and abdomen) and brief neurological examination (mental status, motor system, and sensory system). Also perform brief physical examination focused on the examination of skin and oropharyngeal mucosa for evidence of bleeding and/or bruising (oral [gums] and cutaneous);
- Obtain vital signs (blood pressure, pulse rate, after being supine for 10 minutes, respiratory rate and oral temperature);
- Obtain clinical chemistry, hematology, coagulation, and urinalysis;
- Obtain 12-lead ECG;
- Obtain blood sample for PK analysis. Note: this is an optional sample, if warranted by the PK results from earlier cohort or cohorts;
- Review concomitant medication usage;
- Complete AE assessment (including SAEs) which will be recorded on AE source forms throughout the study and placed in the subject's clinic records. Data from the AE source form will be entered in the EDC system. All AEs will be monitored until they are resolved or determined by the site PI to be medically stable;
- Provide instructions to return on Day 15±1.

7.4 Day 15 ±1 (Final Study Visit)

The following procedures will be performed:

- Complete a physical examination including vital signs (blood pressure, pulse rate, respiration rate, and oral temperature after being supine for 10 minutes), and body weight;
- Obtain serum pregnancy test (females only);
- Obtain clinical chemistry, hematology, coagulation, and urinalysis;
- Obtain vital signs (blood pressure, pulse rate, after being supine for 10 minutes, respiratory rate and oral temperature);
- Obtain 12-lead ECG;
- Fecal occult blood assessment at follow-up will be performed as per discretion of the PI, if positive will continue to follow until resolution;
- Review concomitant medication usage;
- Complete AE assessment (including SAEs) which will be recorded on AE source forms throughout the study and placed in the subject's clinic records. Data from the AE source form will be entered in the EDC system. All AEs will be monitored until they are resolved or determined by the site PI to be medically stable.

A tabulated schedule of events is provided in [Appendix IV](#).

7.5 Early Termination Visit

The clinic will make every effort to perform all assessments outlined for the follow-up visit (Day 15±1) if a subject is terminated prematurely from the study. All information collected will be documented in the subjects study records including eCRF.

7.6 Unscheduled Visits

Data from unscheduled visits or procedures (if any) will be captured in the EDC system and presented in data listings. These data will be clearly identified as unscheduled observations. Safety assessments including updated history and the following onsite evaluations: AE, PE, and any other study procedures deemed necessary by the PI will be obtained.

8 STUDY PROCEDURES/EVALUATIONS

8.1 Clinical Evaluations

During screening, a medical history, including a current medication history, will be obtained by interview and, if available, medical records. Additionally, demographic data, including gender, date of birth, race, and ethnic origin, and a history of alcohol abuse or dependence will be collected at screening.

A complete physical examination, including vital signs, examination of the skin; head, eyes, ears, nose, and throat; lymph nodes; heart; lungs; abdomen; extremities; and joints will be performed at screening and the final follow-up visit. This examination will also include an assessment for stigmata of hepatorenal insufficiency, anemia, coagulopathy, addiction, etc. Breast and genital examinations will not be performed. The complete physical examination will include weight (without shoes and wearing lightest possible clothing). The complete physical examination at screening will also include height and calculation of the BMI and 12-lead ECG. An abbreviated physical examination (general appearance, heart, lungs, skin, and abdomen) and brief neurological examination (mental status, motor system, and sensory system) will be done daily. Additionally, brief examinations focused on skin and mouth for bleeding and/or bruising (oral [gums] and cutaneous) will be performed daily. A targeted physical examination (i.e. hematologic/bleeding and neurological) will be conducted in response to any AE, as determined by the site PI and the grading of the AE will then be determined.

8.2 Laboratory Evaluations

8.2.1 Clinical Laboratory Evaluations

Laboratory assessments will be done at screening, check-in (Day -1), Days 1 through 8, 10 (± 1) and 15 (± 1) unless otherwise noted at approximately the same time each day (within 10 minutes). The following specific tests will be performed as per [Appendix IV](#).

Screening:

- Serology will include hepatitis B surface antigen, antibodies to hepatitis C, and antibodies to HIV.
- Urine: Toxicology screen to include at a minimum marijuana, cocaine, methamphetamine, opiates, phencyclidine, barbiturates, benzodiazepines, tricyclic antidepressants, methadone, and amphetamines. Cotinine level, pregnancy; urine alcohol levels; and urinalysis with microscopic examination;

- Serum: Comprehensive metabolic profile (chemistry 17), complete hepatic panel to include LDH, γ -glutamyltransferase (GGT), AST, ALT and direct and indirect bilirubin. Serum fertility panel to include human chorionic gonadotropin (HCG) to exclude pregnancy and FSH to confirm menopausal/amenorrheic status;
- Hematologic/coagulation: Complete blood count with differential and quantitative PLTs. Coagulation studies will include international normalized ratio (INR), PT, and aPTT. Samples for select hematology (PLT count);
- Fecal Occult Blood Assessment: At screening, subjects will be given a fecal occult blood card with instructions for use and return of the card to the clinic on or before Day -1. This sample will serve as the pre-dose assessment.

Check-in Day -1:

- Urine: Toxicology screen to include at a minimum marijuana, cocaine, methamphetamine, opiates, phencyclidine, barbiturates, benzodiazepines, tricyclic antidepressants, methadone, and amphetamines. Cotinine level, pregnancy; urine alcohol levels; and urinalysis with microscopic examination;
- Serum: Comprehensive metabolic profile (chemistry 17), complete hepatic panel to include LDH, GGT, AST, ALT and direct and indirect bilirubin, and pregnancy;
- Hematologic/coagulation: Complete blood count with differential and quantitative PLTs. Coagulation studies will include INR, PT, and aPTT;
- Fecal Occult Blood Assessment: If not already done, the returned screening test card will be assessed for evidence of fecal occult blood.

The Day -1 laboratory test results (serum chemistry/hematology/urinalysis) are considered as baseline. Laboratory reports will be available before dosing on Day 1 and must be promptly reviewed by the PI. Any subjects having one or more baseline laboratory test results meeting Grade 2 or higher criteria on the toxicity grading scale in [Appendix II](#) are ineligible for study participation.

Days 1 through 8 and follow ups on Day 10 (± 1) and Day 15 (± 1):

- Hematology, clinical chemistry, & coagulation: A subset of hematology (PLT count), serum chemistry (AST, ALT), and coagulation (INR, PT, aPTT) assessments will be collected prior to the first dose only on Day 1. Full clinical chemistry, hematology, coagulation, and urinalysis testing will be performed on Days 2 through 8 and follow ups on Day 10 (± 1) and Day 15 (± 1).

- Fecal Occult Blood Assessment: Fecal occult blood assessments will be performed on Days 1 through 8 and Day 15. If any fecal occult blood test is positive during the study period, subject(s) will be evaluated and a test will be performed on all subsequent stool specimens until negative. If fecal occult blood remains positive (excluding for hemorrhoids) for 3 consecutive samples, subjects will be referred for a GI evaluation and will be withdrawn from the study.
- Vomitus Occult Blood: Occult blood assessments will be done on all vomitus.

All laboratory assessments will be done by the clinical site's certified laboratory. Laboratory toxicity grading will be determined by use of the FDA Guidance for Industry: *Toxicity Grading Scale for Healthy Adult and Adolescent Volunteers Enrolled in Preventive Vaccine Clinical Trials September 2007* and the *Division of Microbiology and Infectious Diseases (DMID) Adult Toxicity Table November 2007*, as modified for this study and appropriate for the administration of UV-4B ([Appendix II](#)).

Table 5: Safety Laboratory Tests

Hematology	Chemistry	Coagulation	Urinalysis	Occult Blood
RBC count	Alkaline phosphatase	INR ^[b]	pH	Fecal
RBC distribution width	ALT ^[b]	PT ^[b]	Specific gravity	Vomitus
WBC count ^[c]	AST ^[b]	aPTT ^[b]	Glucose	
Basophils	Total bilirubin		Ketones	
Eosinophils	Indirect Bilirubin			
Lymphocytes	Gamma-glutamyltransferase		Leukocyte esterase	
Monocytes	Lactate dehydrogenase ^[a]		Nitrites	
Neutrophils	Blood urea nitrogen		Occult blood	
Hematocrit	Creatinine		Protein	
Hemoglobin	Uric acid		RBCs/hpf	
Mean corpuscular hemoglobin	Sodium		WBCs/hpf	
Mean corpuscular hemoglobin concentration	Chloride		Bacteria	
Reticulocyte count	Carbon dioxide		Casts	
MCV	Potassium		Epithelial cells	
Platelet count ^[b]	Creatine phosphokinase ^[a]		Mucous threads	
	Albumin		Crystals	
	Calcium			
	Magnesium			
	Protein (total)			
	Amylase			
	Lipase			

[a] If either lactate dehydrogenase or creatine phosphokinase is elevated (i.e., Grade 2 or higher, or otherwise deemed clinically significant by the PI), iso-enzyme levels will be determined using investigative assays.

[b] Samples for select hematology (PLT count), serum chemistry (AST and ALT), and coagulation (INR, PT, aPTT) assessments will be collected on Day 1 prior to the first dose of study product.

[c] Differential should include absolute values.

8.2.2 Special Assays or Procedures

Blood samples for UV-4 PK analysis will be collected in tubes containing K2EDTA as the anticoagulant on the days specified in [Section 7](#) and [Appendix IV](#). The actual date and time of collection of each sample will be recorded on the appropriate section of the eCRF.

The total volume of blood that will be drawn from each subject in this study is described in [Table 6](#).

Table 6: Volume of blood to be drawn from each Subject

Type	Laboratory Test	Sample Volume (mL)	Number of Samples	Total Volume (mL)
Safety	Clinical chemistry	8.5	11	93.5
	ALT and AST only	3.5	1	3.5
	Hematology	2	11	22
	Coagulation	20.7	11	227.7
	aPTT, PT, INR	2.7	1	2.7
	Platelet count	2.7	1	2.7
	Serology	8.5	1	8.5
	future assays ^[a]	2	1	2
Pharmacokinetic		3	31	93
When using an indwelling catheter 1.0 mL of blood will be removed prior to sample collection		1	31	31
Total		54.6	100	486.6

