14.7 Future Use of Stored Specimens

Any plasma, blood, or urine left after all clinical laboratory testing is done will be discarded. Any plasma left after PK analysis will be stored at Emergent or designee bioanalytical laboratory and used for future research. A separately collected blood sample will be stored at Emergent or designated bioanalytical laboratory [REDACTED]

[REDACTED] At the completion of the protocol, the disposition of samples and data will be per Emergent instructions. Any loss or unanticipated destruction of samples or data will be reported to the IRB. In compliance with subject confidentiality and privacy act (e.g. HIPAA); no genetic testing, including pharmacogenomics, will be done on any stored specimens.

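### Table 6 allots 20.7 mL to each of 11 coagulation draws but 2.7 mL to the Day 1 draw for the same three tests; up to 198 mL per subject is unexplained

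*Protocol*

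**What the plan says.** Section 8.2.2 introduces Table 6 with the words "The total volume of blood that will be drawn from each subject in this study is described in" that table, and its bottom line is 486.6 mL. Two rows concern coagulation: "Coagulation 20.7 11 227.7" and "aPTT, PT, INR 2.7 1 2.7".

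The content of the panel is set out in Section 8.2.1. For check-in it says "Coagulation studies will include INR, PT, and aPTT", and screening names the same three. The coagulation column of Table 5 lists those three and nothing else, and each carries footnote [b], which says that "coagulation (INR, PT, aPTT) assessments will be collected on Day 1 prior to the first dose of study product". For later days, "Full clinical chemistry, hematology, coagulation, and urinalysis testing will be performed on Days 2 through 8", and again on Days 10 and 15.

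On leftover and stored blood, Section 14.7 says "Any plasma, blood, or urine left after all clinical laboratory testing is done will be discarded" and "A separately collected blood sample will be stored at Emergent or designated bioanalytical laboratory". Table 6 has its own 2 mL row for future assays.

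The documents disagree about Day 1. Section 8.2.1 and footnote (g) of Appendix IV confine it to a pre-dose subset. Section 7.3.1 lists chemistry, hematology and coagulation among the procedures that follow dosing.

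**The concern.** One panel of three tests has two volumes, 20.7 mL and 2.7 mL, a ratio of 7.7. The larger is multiplied by 11 and makes coagulation the biggest item in the table, well ahead of the pharmacokinetic samples (93 mL).

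The table is the protocol's statement of how much blood each healthy volunteer gives. As written, there are three possibilities: the stated total is too high; blood is taken for tests the protocol does not name; or 20.7 mL is a collection volume whose reason is not given. A site following the table would draw the larger amount.

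There is also a modest link to safety data. Appendix II grades haemoglobin on its fall from baseline (Grade 1 up to 1.5 g/dL, Grade 2 at 1.6 to 2.0, Grade 3 at 2.1 to 5.0). Section 9.6 halts the study for the same Grade 2 event in three or more subjects of a cohort, or for any single Grade 3 finding apart from its aPTT exception. Blood drawn for the study lies on the path to those grades.

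**Working it through.** **1. Reproduce Table 6.** Each row is number of samples × mL per sample.
- Chemistry: 11 × 8.5 = 93.5
- Day 1 ALT/AST: 1 × 3.5 = 3.5
- Hematology: 11 × 2 = 22
- Coagulation: 11 × 20.7 = 227.7
- Day 1 coagulation subset: 1 × 2.7 = 2.7
- Day 1 platelet count: 1 × 2.7 = 2.7
- Serology: 1 × 8.5 = 8.5
- Future assays: 1 × 2 = 2
- Pharmacokinetic: 31 × 3 = 93
- Catheter discard: 31 × 1 = 31

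The columns sum to 54.6 mL, 100 samples and 486.6 mL, as printed. A misread 20.7 would break the row product and two of the column sums, so the figure is really in the table.

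**2. Count the draws.** From Section 8.2.1 and Appendix IV: screening 1 + Day -1 1 + Days 2 to 8 7 + Day 10 1 + Day 15 1 = 11, which matches the table. If the Section 7.3.1 entry were a further full draw, the count would be 12.

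**3. Share of the total.** The eight safety rows sum to 362.6 mL, of which the other seven make up 362.6 − 227.7 = 134.9 mL. The coagulation row is 227.7 / 362.6 = 63% of safety blood and 227.7 / 486.6 = 47% of all blood.

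**4. The gap.** (20.7 − 2.7) × 11 = 18 × 11 = 198 mL; 198 / 486.6 = 41%. With 12 draws it would be 18 × 12 = 216 mL.

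**5. If 2.7 mL is enough.** Row: 2.7 × 11 = 29.7 mL. Total on the rows now in the table: 486.6 − 198 = 288.6 mL. Serum pregnancy and FSH samples have no row, so 288.6 mL would still be incomplete for subjects who have those tests.

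**6. Look for an explanation in the documents.**
- Stored blood: a separate sample under Section 14.7, with its own 2 mL row.
- Platelet function testing, removed by Amendment 2: the log shows that it had its own row (4.5 mL × 2).
- Chemistry, hematology, serology, pharmacokinetics and catheter discard: each has its own row.
- Serum pregnancy and FSH: these concern females only, at a few visits, so they cannot account for 18 mL at every draw in every subject.
- Fibrinogen: graded in Appendix II, but listed in neither Section 8.2.1 nor Table 5, so it is not a stated purpose.

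**7. Timing against haemoglobin.** Day 1 has only a platelet count in the Section 8.2.1 subset, so the Day -1 haemoglobin is the scheduled baseline. Between the Day -1 and Day 8 samples lie the coagulation draws of Days 2 to 7 (six), plus either the Day -1 or the Day 8 draw, depending on which tube is filled first. That makes seven: 7 × 18 = 126 mL.

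**The case against.** The best reply is that 2.7 mL is a poor benchmark. Table 6's Day 1 volumes do not scale with content: a platelet count alone has 2.7 mL, while full hematology has 2 mL. Specimen instructions are left to a laboratory manual that is not among the documents, so 20.7 mL could be a collection requirement for exactly these three tests. Nor is Table 5 a closed list. Direct bilirubin is in Section 8.2.1 but not in Table 5, and Appendix II grades serum glucose and phosphorus, which the chemistry column omits. Silence about further coagulation tests is therefore weak evidence that none is run. All of this stands, and it is why the 198 mL can only be called unexplained.

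It is also fair that Table 6 is nearer to a planned maximum than a measured draw. Its 31 pharmacokinetic samples include the Day 10 sample, which Section 7.3.4 makes optional, and the discard row applies only with an indwelling catheter. That bears on 486.6 mL as a total but not on the mismatch between the two coagulation rows.

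The 11-draw count is open to challenge through Section 7.3.1. The count agrees with Section 8.2.1 and Appendix IV, but the conflict is real and must be resolved.

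Finally, no objective, outcome measure, analysis or rule is set from Table 6, and the documents state no blood-volume limit. That keeps the point minor. It does not remove an inconsistency in what the protocol says will be taken from volunteers.

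**Conclusion.** The inconsistency holds. Table 6 gives two volumes to the same three tests, and no current passage accounts for the 18 mL difference: up to 198 mL per subject, 41% of the stated total. This rests on 11 draws and on 2.7 mL as the comparison figure, which is the table's own and is not shown to be the right volume. If 20.7 mL is really drawn, about 126 mL of the difference falls between the baseline and Day 8 haemoglobin samples and could contribute to grades that feed the halting rules.

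A reader might infer more, and the documents do not support it:
- That 20.7 is a slip for 2.7, or that 198 mL is surplus. Nothing shows which volume is intended.
- That the table is wrongly added. It is not.
- That a blood-volume limit is breached. None is stated.
- That the haemoglobin comparison is biased. The extra draw would be the same in active and placebo subjects, and the documents give no figure from which to size its effect on haemoglobin.

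Severity: minor.

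**What to change.** Reconcile the Table 6 coagulation row with Section 8.2.1 and Table 5.

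- If 2.7 mL is enough for the three tests, set the row to 29.7 mL, draw only that, and reduce the total by 198 mL. That gives 288.6 mL on the present rows, before adding the serum pregnancy and FSH samples that have no row.
- Otherwise, state what the 20.7 mL is for: further tests, named in Table 5 (saying whether fibrinogen is one), or a laboratory collection requirement.

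In the same amendment, reconcile the Day 1 post-dose entry in Section 7.3.1 with Section 8.2.1 and Appendix IV, so that the number of draws is settled. Carry the reconciled total into every document that repeats it.

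The cost is one table row and one total, or a line of explanation, plus one bullet in Section 7.3.1. No planned analysis changes.
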